## APPENDIX 1 – ASA PHYSICAL STATUS CLASSIFICATION SYSTEM\*

- ASA Physical Status 1** - A normal healthy patient
- ASA Physical Status 2** - A patient with mild systemic disease
- ASA Physical Status 3** - A patient with severe systemic disease
- ASA Physical Status 4** - A patient with severe systemic disease that is a constant threat to life
- ASA Physical Status 5** - A moribund patient who is not expected to survive without the operation
- ASA Physical Status 6** - A declared brain-dead patient whose organs are being removed for donor purposes

\* These definitions appear in each annual edition of the [ASA Relative Value Guide](#)

**Study Title:** Multi-site Anesthesia randomized controlled Study of End tidal control (Et Control) compared to conventional anesthesia Results (MASTER-Anesthesia Trial)  
**Study No:** 123.07-2015-GE5-0002

GE Healthcare

## APPENDIX 2 – EXTRACTION ALGORITHM

A high level description of the extraction algorithm is provided below. The extraction algorithm is common to both operational modes (Et Control and Control) for the derivation of user desired end-tidal concentrations for anesthetic agent or oxygen. In addition to derived user desired end-tidal concentrations with the algorithm, the clinicians also record desired end-tidal concentration values during the case. The extraction algorithm analyzes the end tidal oxygen performance separately from the end-tidal anesthetic agent performance.

Although this extraction algorithm provides an objective comparison between Et Control and Control group, it cannot be used as an engineering analysis of the Et Control controller. The biggest reason for this is described in Step 4 (below). Instead of analyzing all of the Et Control set target end-tidal values directly, smaller setting changes are combined and treated as one step change. This combination of setting changes leads to a more conservative assessment of Et Control.

The extraction algorithm steps are as follows:

- 1) Identify all device setting changes. The device setting changes in the Fresh Gas control mode are the total mixer flow, mixer oxygen concentration and vaporizer concentration settings. Any mixer and vaporizer setting changes are interpreted as a user attempt to alter the patient end tidal agent or oxygen concentration. In the Et Control mode, patient end tidal concentration is targeted directly by adjusting the set end tidal agent and oxygen concentration. Et Control commands the changes to the mixer and vaporizer to alter the patient end tidal concentrations.
- 2) Determine whether a device setting change is 'Significant' in magnitude. The criteria for significance is whether the subsequent measured response 2 minutes following the device setting change causes a 0.9 %v/v, 0.31 %v/v or 0.17 %v/v change for Desflurane, Sevoflurane or Isoflurane, respectively, or 5 %v/v for oxygen.
- 3) Identify all periods of end tidal concentration measurement stability, following setting changes (i.e. Steady States). A stable period for agent is defined as all points where the rate of change of measured EtAA is less than 0.2 %v/v per minute and persists for a period of 2 minutes. A stable period for oxygen is defined as all points where the rate of change of the measured EtO2 is less than 1.5 %v/v per minute and persists for a period of one minute.
- 4) Determine the desired end tidal concentration by averaging all EtAA or EtO2 points once stability is reached until the next significant setting change. Non-significant changes are ignored and treated as part of the current step change/steady state.
- 5) For all significant changes which reach a stable concentration, compute the efficacy performance statistics (Response Time, Command Overshoot, Settling Time, Steady State Mean and Standard Deviation).
  - a. Response Time for agent is defined as the smaller of either the time to reach 90% of the change between the initial EtAA and the desired end tidal concentration or the

**Study Title:** Multi-site Anesthesia randomized controlled Study of End tidal control (Et Control) compared to conventional anesthesia Results (MASTER-Anesthesia Trial)  
**Study No:** 123.07-2015-GES-0002

GE Healthcare

time to get to within 0.9 %v/v, 0.31 %v/v or 0.17 %v/v for DES, SEV or ISO, respectively, of the desired end tidal concentration.

- b. Response Time for oxygen is defined as the smaller of either the time to reach 90% of the change between the initial EtO2 and the desired end tidal concentration or the time to get to within 5 %v/v of the desired end tidal concentration.
- c. Command Overshoot is defined as the maximum value beyond the desired end tidal concentration from the start of the step change until the Settling Time.
- d. Settling Time for agent is determined by looking backwards from the stable concentration to the time where the agent is within 0.9 %v/v, 0.31 %v/v and 0.17 %v/v for DES, SEV and ISO, respectively, of the desired end tidal concentration.
- e. Settling Time for oxygen is determined by looking backwards from the stable concentration to the time where the oxygen is within 5 %v/v of the desired end tidal concentration.

**Study Title:** Multi-site Anesthesia randomized controlled Study of End tidal control (Et Control) compared to conventional anesthesia Results (MASTER-Anesthesia Trial)

**Study No:** 123.07-2015-GES-0002

GE Healthcare

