  10. Time subject is moved from the operating room (OR)
  11. Assessment of adverse events – throughout the study
- ◆ Electronic data collection by the Aisys CS machine log:
    1. If Et Control was activated, the time of activation will be recorded
    2. EtO2, EtCO2, EtAA, FIAA and FiO2 (this data will be collected breath to breath)
    3. Anesthesia machine settings, alarms and events
  - ◆ Calculation of the data collected from the Aisys CS machine log
    1. Time of last breath (point of last breath from the data collection)
    2. Anesthetic agent usage

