### 8.1.2 Statistical Methods Overview

Data collected in this study will be presented using summary tables, data listings and graphs. Study endpoints and parameters will be summarized using descriptive statistics.

The descriptive statistics for continuous variables will include mean, standard deviation, median, Q1 and Q3, minimum, maximum, and sample size. Categorical variables will be described with counts, percentages, and sample size.

For comparison (between arms or against null values), categorical variables will be tested using appropriate contingency table analyses (exact or chi-square approximations), and continuous variables will be tested using Student's t-test or non-parametric methods, depending on variable distribution. P-values will be presented to three decimal places and p-values less than .001 will be presented as '<.001.'

**Study Title:** Multi-site Anesthesia randomized controlled Study of End tidal control (Et Control) compared to conventional anesthesia Results (MASTER-Anesthesia Trial)  
**Study No:** 123.07-2015-GES-0002

GE Healthcare

Subjects using different anesthetic agents will be pooled for analysis per the arm they are randomized. Separate analysis may be performed by anesthetic agent when pooling data across anesthetic agents is not appropriate.

No imputation will be performed for missing data unless specified otherwise.

A data extraction algorithm is used to identify periods of end tidal concentration measurement stability following setting changes (i.e. Steady States) during a case, as well as to measure response times, settling times, and overshoot amounts from these steady states in order to compare across arms. The extraction algorithm is not part of the statistical analysis, but provides the above-mentioned endpoints. (See Appendix 2 – Extraction algorithm for more information on the extraction algorithm.)

There will be two scenarios in defining a step change and steady state when performing the data extraction: 1) *using the data extraction algorithm to determine the desired end-tidal concentrations of anesthetic agent and oxygen for both arms* (See Appendix 2 – Extraction algorithm for more information on the extraction algorithm); 2) *using the clinicians recorded end tidal target values of anesthetic agent and oxygen for the Control arm, and the set target value for the Et Control arm.*

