### 8.3 Handling of Missing Data

In general, data analysis will be performed on the basis of all available data.

For missing values of primary endpoints, multiple imputations will be performed and sensitivity analysis will be conducted for primary endpoints. The multiple imputation will be performed with SAS PROC MI, using the regression method for monotone missing pattern, with the covariates treatment arm, clinician, anesthetic agent, and subject ASA status as the independent variables. A total of 5 imputed data sets will be generated and analysis of primary endpoints will be performed on each imputed data set. PROC MIANALYZE will be used to summarize the results from imputed data sets.

Clinician recorded end tidal target values are considered missing, when a recorded target is not available for a setting adjustment resulting in a significant change in end tidal measurements. If the change in end tidal measurement results in more than 5% v/v O2, 0.9% v/v DES, 0.31% v/v SEV, or 0.15% v/v ISO from the previous end tidal measurement over a period of 2 minutes, then the recorded target data is considered missing. This portion of the data is not used for the purpose of the analysis with the clinician recorded target values.

**Study Title:** Multi-site Anesthesia randomized controlled Study of End tidal control (Et Control) compared to conventional anesthesia Results (MASTER-Anesthesia Trial)  
**Study No:** 123.07-2015-GE5-0002

GE Healthcare

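### The isoflurane change cut-off is 0.15 %v/v in Section 8.3 but 0.17 %v/v in Appendix 2; secondarily, one EtAA stability rate serves all three agents

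*Combined protocol and SAP*

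**What the plan says.** **Change cut-offs.** Appendix 2, step 2 treats a setting change as significant if, 2 minutes later, it "causes a 0.9 %v/v, 0.31 %v/v or 0.17 %v/v change for Desflurane, Sevoflurane or Isoflurane, respectively", or 5 %v/v for oxygen. Steps 5a and 5d use the same three agent values as the response and settling bands; in 5d, for example, settling is reached when "the agent is within 0.9 %v/v, 0.31 %v/v and 0.17 %v/v for DES, SEV and ISO, respectively" of the desired value. Section 8.3 says when a clinician's recorded target counts as missing, in which case that stretch of data is left out of the recorded-target analysis. Its cut-offs are 5 %v/v for oxygen, 0.9 for desflurane and "0.31% v/v SEV, or 0.15% v/v ISO from the previous end tidal measurement over a period of 2 minutes".

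**Where they act.** The primary analysis (Section 8.1.3) consists of scenario 1, in which the algorithm derives the desired concentration in both arms, and scenario 2. Section 8.1.2 bases scenario 2 on "recorded end tidal target values of anesthetic agent and oxygen for the Control arm, and the set target value for the Et Control arm".

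**Stability.** Appendix 2, step 3 counts EtAA as stable "where the rate of change of measured EtAA is less than 0.2 %v/v per minute and persists for a period of 2 minutes", with no split by agent. Step 4 takes the desired concentration as the average of all "points once stability is reached until the next significant setting change". The acceptance limits in Section 3.4.1 are agent-specific: the larger of 5% of the steady-state value and 0.6 (Des), 0.2 (Sev) or 0.1 (Iso) %v/v.

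**The concern.** **Cut-off.** Both rules describe a significant change after a setting adjustment, over the same 2 minutes, and three of the four values are identical. Only isoflurane differs, and no reason is given. Recorded targets are used for the Control arm only, so the Section 8.3 exclusion acts on one arm. At stake is which Control arm isoflurane data enter half of the primary analysis. If this is left open, the choice could be made after the data are in hand.

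**Stability rate.** In scenario 1 the steady state supplies both the reference value and the denominator of the primary endpoint. A rate that is strict relative to the desflurane limit is loose relative to the isoflurane limit, so the end of a transition can be counted as steady state and then scored as out of limits. Agents are pooled by arm (Section 8.1.2), and agent is not a stratification factor (Section 6.1), so the score could depend partly on agent mix and on speed of response.

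**Working it through.** **1. The two sets of cut-offs (%v/v over 2 minutes)**

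| | Des | Sev | Iso | O2 |
|---|---|---|---|---|
| Appendix 2, step 2 | 0.9 | 0.31 | 0.17 | 5 |
| Section 8.3 | 0.9 | 0.31 | 0.15 | 5 |

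The gap is 0.17 − 0.15 = 0.02 %v/v, about 12% of 0.17. An unrecorded isoflurane change of 0.16 %v/v is below 0.17, so scenario 1 treats it as part of the current steady state. It is above 0.15, so scenario 2 treats the target as missing and discards the data.

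**2. Which value fits the rest of the plan**

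The 1-MAC values are in the footnote to Section 2.1.3: Des 6.0, Sev 2.1, Iso 1.15 %v/v.
- 0.15 × 6.0 = 0.90; 0.15 × 2.1 = 0.315; 0.15 × 1.15 = 0.1725. These match 0.9, 0.31 and 0.17.
- 0.15 / 1.15 = 0.130 MAC, which breaks the pattern.
- Table 1-1 also uses ±0.15 MAC as the EtAA steady-state deviation limit.
- A rival pattern is 1.5 times the acceptance limit: 0.90, 0.30 and 0.15. It gives 0.15 for isoflurane but misses the printed sevoflurane value of 0.31.

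**3. Worst-case drift inside a stable window**

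The greatest 2-minute excursion is 0.2 × 2 = 0.4 %v/v. For a straight-line drift about its own mean, the largest deviation is 0.4 / 2 = 0.2 %v/v, and the share of time within limits is min(1, limit / 0.2).
- Des: 0.6 / 0.2, capped at 100%.
- Sev: 0.2 / 0.2 = 100%.
- Iso: 0.1 / 0.2 = 50%.

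The fixed limits apply here because 5% of the steady state exceeds them only above 12% (Des), 4% (Sev) or 2% (Iso).

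**4. The tail of a step change**

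Assumptions: a first-order approach to target, with the Table 1-1 EtAA response times read as 90% times. Then the time constant is τ = t90 / ln 10, and the distance still to go when the rate falls to 0.2 is 0.2 × τ.

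| t90 | τ (min) | Distance left (%v/v) | ÷ limit: Des | Sev | Iso |
|---|---|---|---|---|---|
| 59 s (average, one site) | 0.427 | 0.085 | 0.14 | 0.43 | 0.85 |
| 78 s (average, other site) | 0.565 | 0.113 | 0.19 | 0.56 | 1.13 |
| 240 s (specification limit) | 1.737 | 0.347 | 0.58 | 1.74 | 3.47 |

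Single steps of 0.25 to 0.5 MAC from 0.8 MAC, held for 15 to 60 minutes, were scored as the percentage of steady-state points within limits of the steady-state mean.
- 59 s: 100% for all three agents.
- 78 s: Des and Sev 100%; Iso 99.65 to 99.92%, a loss of at most 0.35 points.
- 240 s: Des 100%; Sev 95.4 to 98.5%; Iso 89.0 to 97.2%.

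**5. Rates scaled to the acceptance limit**

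For desflurane, rate / limit = 0.2 / 0.6 = 1/3 per minute. The same ratio gives 0.2 / 3 = 0.067 (Sev) and 0.1 / 3 = 0.033 (Iso) %v/v per minute. At 240 s the distance left is then 1.737 / 3 = 0.58 times the limit for every agent. Rates tied to the step 2 cut-off, 0.31 / 2 = 0.155 and 0.17 / 2 = 0.085, would leave 0.155 × 1.737 / 0.2 = 1.35 (Sev) and 0.085 × 1.737 / 0.1 = 1.48 (Iso) times the limit, so they would not remove the tail.

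**The case against.** **On the cut-off,** one can argue that Section 8.3 and Appendix 2 are separate rules for separate scenarios and need not agree. The identical window and the three identical values make that unlikely, and no rationale is offered. What stands is that the consequence is narrow: unrecorded isoflurane changes between 0.15 and 0.17 %v/v.

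**On the stability rate,** the case against is stronger, and much of it stands.
- The rule contradicts nothing in the plan. It is common to both arms, and Appendix 2 calls itself a high-level description.
- A reader might divide 0.4 %v/v by the limits and infer that a stable window can breach the sevoflurane limit twofold and the isoflurane limit fourfold. That sets a full excursion against a half-width. About its own mean, the worst-case window stays within limits for sevoflurane, and half the time for isoflurane.
- A reader might infer from the 240 s scores that the primary result is materially distorted. But 240 s is a permissible limit and was not an observed average. Table 1-1 covers Et Control only, and the text beneath it names only sevoflurane and desflurane. The plan's own response time (step 5a) is the shorter of the 90% time and the time to come within a fixed band, so the time constants are themselves uncertain.
- A reader might infer that the rule favours Et Control, because Section 1.2.3 reports that it responded faster on average in the feasibility study. Equal application does not guarantee equal effect, but no Control response times are given, so neither direction nor size follows.
- Section 8.1.2 permits separate analysis by agent, and scenario 2 uses recorded or set targets in place of the algorithm's. Both are partial checks, though the first is only permissive.

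**Conclusion.** The cut-off mismatch is an error in current text and should be corrected. It is small, limited to isoflurane, and acts on Control arm data in scenario 2. The better supported value is 0.17 %v/v. That is an inference from the MAC scale, because the plan does not say how the cut-offs were derived.

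The single stability rate is a secondary design weakness. At the Table 1-1 averages the single-step loss is nil for desflurane and sevoflurane and at most about 0.35 points for isoflurane. It becomes material for sevoflurane and isoflurane only near 240 s. These figures rest on a first-order response and on reading Table 1-1 as 90% times. They describe one step and are not trial-level effects. How often slow responses occur, and what they do to the difference between arms, cannot be derived from the documents.

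**What to change.** 1. Use one isoflurane cut-off in Section 8.3 and in Appendix 2 steps 2, 5a and 5d, fixed before the machine logs are extracted. The proposed value is 0.17 %v/v, subject to the sponsor's confirmation. Cost: one figure.

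2. Keep the common stability rate for the primary analysis. Before unblinding, pre-specify one scenario 1 sensitivity extraction with rates tied to the acceptance limit, for example 0.2 (Des), 0.067 (Sev) and 0.033 (Iso) %v/v per minute. State how the rate is computed or smoothed, since Appendix 2 does not. Report by arm and agent how many steady states start later or are lost.

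The cost is one extra extraction run and a short specification. There is a real downside. The signal is breath-level (Section 6.3.2: "this data will be collected breath to breath"), and step 5 works only on changes that settle: "For all significant changes which reach a stable concentration, compute the efficacy performance statistics". Stricter rates may therefore drop slow or noisy periods, possibly unequally by arm. For that reason they belong in a sensitivity analysis, read together with the counts of lost steady states, and should not replace the primary rule.

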#### High Flow Anesthesia – Non Rebreathing

Inspired gas comes totally from fresh gas

High gas flow in excess of metabolic uptake is scavenged

[figure not shown]

Figure 1-2: High Flow Anesthesia – Non-rebreathing

In low flow anesthesia (LFA) practice where the FGF is lower than the patient minute ventilation, expired patient gases are recirculated. After carbon dioxide is removed, these

**Study Title:** Multi-site Anesthesia randomized controlled Study of End tidal control (Et Control) compared to conventional anesthesia Results (MASTER-Anesthesia Trial)  
**Study No:** 123.07-2015-GE5-0002

GE Healthcare

recirculated gases combine with the fresh gas to form the patient inspired gases, see Figure 1-3. This recirculated patient gas mixes and dilutes the vaporizer anesthetic output concentration, and adds another layer of difference and uncertainty between the set vaporizer anesthetic output concentration and the MAC dosage prescribed for the patient. This decoupling increases as the fresh gas flow rate (FGFR) is decreased relative to the patient minute ventilation. More so than in HFA, the vaporizer setting must be adjusted frequently to align the measured end tidal anesthetic concentration to achieve the prescribed concentration dosage. At lower FGF and greater dilution by the recirculated gases, the challenge for the clinician is to achieve and maintain the patient's prescribed drug dosage.

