#### **8.1.4 Analysis of Secondary Endpoints**

##### **8.1.4.1 Performance Statistics**

For response time, settling time and overshoot amount (% to steady state mean for anesthetic agent, and v/v for O2), analysis will be on the basis of each steady state. The arithmetic average of all steady states will be calculated and be compared between the Et Control Arm and the Control Arm using t-test. Subjects with at least 1 overshoot amount greater than 10%, 20%, or 30% of steady state concentration will be counted and compared between the two arms using Fisher exact test.

For average deviation (% to steady state mean for anesthetic agent, and v/v for O2) and half width of 95% CI of deviation, analysis will be on the basis of each subject. The weighted average using the duration of steady state duration as the weight for a subject will be calculated and compared between the Et Control and Control Arms using t-test. For the maximum deviation (% to steady state mean for anesthetic agent, and v/v for O2), the maximum of all steady states for a subject is taken for analysis, and the maximum deviation be compared between Et Control and Control arms using nonparametric Wilcoxon rank sum method.

The analysis of above performance statistics will be performed by different ASA status.

**Study Title:** Multi-site Anesthesia randomized controlled Study of End tidal control (Et Control) compared to conventional anesthesia Results (MASTER-Anesthesia Trial)  
**Study No:** 123.07-2015-GES-0002

GE Healthcare

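### Scenario 1 drops a Control step and its overshoot when the clinician makes a significant correction before stability, but keeps the same trace whole when the Et Control controller makes the correction

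*Combined protocol and SAP*

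**What the plan says.** Appendix 2 (Extraction algorithm) produces response time, settling time and overshoot in scenario 1. Four of its rules matter here.

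- **Step 1, what counts as a setting change.** For conventional delivery, "The device setting changes in the Fresh Gas control mode are the total mixer flow, mixer oxygen concentration and vaporizer concentration settings". In Et Control mode the setting change is the user's new end-tidal target, after which "Et Control commands the changes to the mixer and vaporizer to alter the patient end tidal concentrations". The controller's own adjustments are therefore not setting changes.
- **Step 2, significance.** The test looks at how far the measured value has moved: "whether the subsequent measured response 2 minutes following the device setting change causes a 0.9 %v/v, 0.31 %v/v or 0.17 %v/v change". Those three figures apply in turn to desflurane, sevoflurane and isoflurane; the oxygen cut-off is 5 %v/v.
- **Step 4, the period.** The desired concentration is averaged "once stability is reached until the next significant setting change". Non-significant changes stay inside the current step.
- **Step 5, what is scored.** "For all significant changes which reach a stable concentration, compute the efficacy performance statistics (Response Time, Command Overshoot, Settling Time" and the steady-state statistics. Step 5c takes overshoot as the "maximum value beyond the desired end tidal concentration from the start of the step change until the Settling Time".

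Section 8.1.4.1 compares the arms by t-test on averages over steady states. It adds a Fisher exact comparison: "Subjects with at least 1 overshoot amount greater than 10%, 20%, or 30% of steady state concentration will be counted".

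Section 3.4.1 names these three endpoints, together with the primary endpoints, as the evidence on achieving and maintaining concentration. Sections 3.4.2 and 8.1.2 also call for a second extraction (scenario 2), using clinician-recorded targets in the Control Arm and set targets in the Et Control Arm.

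**The concern.** A significant change that is overtaken by another significant change before stability never reaches a stable concentration of its own. On the natural reading of steps 4 and 5 it yields no statistics, and the clock and starting value move to the later change.

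The rule is worded alike for both arms but acts on different events. A Control clinician who turns the vaporizer up, overshoots and turns it down has logged two setting changes. An Et Control user whose controller produces the same curve has logged one. Section 1.1.3 says of low-flow practice that "the vaporizer setting must be adjusted frequently to align the measured end tidal anesthetic concentration", so repeated Control adjustment is to be expected.

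At stake are the between-arm tests on settling time, overshoot and response time, and the counts of subjects with large overshoots. Appendix 2 presents the algorithm as an even-handed comparison. Its one remark on direction, that pooling small changes is conservative for Et Control, does not cover the restart at a significant correction.

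**Working it through.** The plan states no figure on this point, so there is none to reproduce. The check applies steps 2 to 5 to one trace logged in two ways.

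**Inputs from Appendix 2.** Cut-off 0.9 %v/v for desflurane at 2 min; stability below 0.2 %v/v per minute for 2 min; settling band 0.9 %v/v; response is the earlier of 90% of the change or entry into that band.

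**Assumptions, not in the documents.** First-order response with time constant τ, no measurement noise, 12 breaths per minute.

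**Example 1: overshoot, then correction.** Start 3 %v/v, peak 7.74 at 2 min, then corrected towards 6; τ = 2 min.

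- Level driving the rise: (7.74 − 3e⁻¹)/(1 − e⁻¹) = 10.5.
- Is the correction significant? Movement in 2 min = 1.74 × (1 − e⁻¹) = 1.10, which exceeds 0.9, so yes.
- Was the first step stable? No. EtAA was still rising at (10.5 − 7.74)/2 = 1.4 %v/v per minute, so the first step is dropped in the Control log.
- Time from correction to band: 2 ln(1.74/0.9) = 1.32 min.
- Time from the first change to 5.1 %v/v: 2 ln(7.5/5.4) = 0.66 min.

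With the desired level at exactly 6, overshoot is 1.74/6 = 29%, settling is 2 + 1.32 = 3.32 min against 1.32, and response is 0.66 min against 1.32. Appendix 2 instead averages the stable period, which puts the desired level at about 6.05 on a 20-minute trace. Breath by breath this gives:

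| | One target change (Et Control log) | Two adjustments (Control log) |
|---|---|---|
| Overshoot | 28% | 0% |
| Settling, min | 3.25 | 1.25 |
| Response, min | 0.75 | 1.25 |

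Control's response time is longer because the correction itself becomes the scored step.

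**Example 2: staged titration.** Desflurane from 2 %v/v, driven towards 4, then towards 6 from 2 min; τ = 2 min.

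- At 2 min EtAA is 4 − 2e⁻¹ = 3.26. It has moved 1.26 (significant) and is still rising at 0.74/2 = 0.37 per minute (not stable), so the first stage is dropped.
- The second stage moves 2.74 × (1 − e⁻¹) = 1.73 in 2 min (significant) and enters the band after 2 ln(2.74/0.9) = 2.2 min.
- Response and settling are both 4.2 min in the one-change log and 2.2 min in the Control log. Here Control's response time is shorter.

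**When an overshoot is erased.** If the correction aims at the final level, an overshoot of size h is erased when h(1 − e^(−2/τ)) ≥ 0.9, that is h ≥ 0.9/(1 − e^(−2/τ)). Section 8.1.4.1 counts overshoot relative to steady state, so h is divided by that level:

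| τ, min | h, %v/v | at 6 %v/v | at 4 %v/v | at 3 %v/v |
|---|---|---|---|---|
| 1 | 1.04 | 17% | 26% | 35% |
| 1.5 | 1.22 | 20% | 31% | 41% |
| 2 | 1.42 | 24% | 36% | 47% |
| 3 | 1.85 | 31% | 46% | 62% |

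**Sevoflurane check.** Start 1.0 %v/v, driven towards 4.0, corrected to 2.0; cut-off 0.31; τ = 1.5 min.

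- Peak 2.6: overshoot 30% against 0%, settling 2.12 against 0.97 min, response 0.40 against 0.97 min (one target change against two adjustments).
- Peak 2.4: the correction is not significant, and both logs give overshoot 20% and settling 1.33 min.

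**The case against.** Several stronger readings are tempting, and the documents do not support them.

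- *Every corrected Control overshoot is deleted.* No. Step 4 keeps a correction below the cut-off inside the current step. At desflurane 3 to 4 %v/v many overshoots above 20%, and some above 30%, would be kept.
- *Et Control steps are always scored in full.* No. A second significant target change before stability drops an Et Control step too.
- *Control always looks faster.* No. Example 1 lengthens its response time.
- *One intended Control change usually takes several significant adjustments.* Section 1.1.3 does not say this, and the feasibility study in Section 1.2.3 reports similar interactions per case, 26 ± 8.7 with Et Control and 26 ± 12.6 in Control.
- *The rule flatters the sponsor's device.* For settling and overshoot it works against Et Control.

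It can also be said that Appendix 2 is a high-level description that never states what happens to a superseded change. That is fair, since dropping it is an inference. If both changes were instead scored against the same final level, the large overshoot would survive in the subject counts. The correction would still add a short, zero-overshoot row to the Control averages.

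Scenario 2 may avoid the problem where the recorded target is unchanged. However, Section 8.3 sets aside data after a significant adjustment with no recorded target, and scenario 1 results are required regardless.

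**Conclusion.** The concern holds in a conditional form. Under scenario 1, steps 1, 4 and 5 can give identical traces different scores by arm whenever a Control correction passes the step 2 cut-off before stability. Settling time and overshoot are then biased in Control's favour, and response time can go either way. For time constants of 1 to 3 min, the overshoot at which erasure begins is about 17–31% of steady state at desflurane 6 %v/v, 26–46% at 4 and 35–62% at 3. That overlaps the range the over-20% and over-30% counts are meant to detect.

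The sizes rest on an assumed noise-free first-order response, and the documents give nothing from which to estimate frequency.

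A reader might infer that the non-inferiority result is compromised. It is not: these endpoints lie outside the primary analysis, the fixed test sequence in Section 8.1.2 and the pass criterion in Section 8.4. The point is still worth acting on, because the primary endpoints score only steady state and these three carry the evidence on reaching the target.

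**What to change.** In Appendix 2 step 5, state how a significant change superseded before stability is handled. Keep the current scoring and prespecify a second analysis of the same three endpoints in both arms:

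- Treat consecutive significant changes not separated by a stable period as one chain.
- Start the clock and take the initial value at the first change of the chain.
- Use the next stable level as the desired concentration.

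Report by arm the number of superseded changes, of chains, and of chains that never stabilise. If the two scorings disagree, draw no between-arm conclusion on speed or overshoot from scenario 1 alone.

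The cost is a few lines of extraction code and a short addition to Appendix 2, with no new data. There is one real drawback. A genuine change of intent before stability is timed as one longer step, and this may fall more often on the Control Arm, where three inputs count as setting changes. Chain scoring should therefore be shown beside the current scoring and not replace it.
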